3.1 Cameroon COVID-19 Situation

Given the changing COVID-19 situation, we will do our utmost to guarantee the safety of participating staff, implementation facilities, and communities. Prior to launching the pilot study, the in-charge of each selected facility will be briefed on the purpose of the pilot study as well as the risks and benefits of participating during the COVID-19 pandemic. The in-charge will grant permission for the pilot study to occur, or request that the facility be excluded due to the burden of COVID-19 pandemic and limited HCW staff. Such decisions to exclude facilities will also occur along with key government officials. In addition, prior to travelling for community visits, study staff will contact community leaders and key community contacts through telephone calls, where possible, to discuss the pilot study and assess the communities' willingness to have non-community members come to conduct a visit. Any formal requests for information or permission will be respected and followed.

Throughout this proposal we have outlined contingency plans for each intervention activity and data collection procedure. We will conduct weekly reviews and work from a decision framework that reviews multiple sources. The decision framework includes:

- **Review government recommendations and restrictions:** If the government has institutionalized closures or the National Ethics Committee recommends research to be suspended, we will not proceed. Instead, we will continue remote data collection where possible, but hold off on further implementation.
- Review of Imperial model estimation of Rt: The model currently estimates for 6-week forecasts. We will review the current transmission rate from this model listed in the weekly Imperial situation reports. If the rate reaches above 1, we will consider suspending the pilot study implementation. For comparison, we will also compare the Cameroon Rt to other African countries. If we decide to suspend activities, we may continue remote data collection where possible, but hold off on further implementation.
- **Review of the Imperial model and IHME projections**: In addition to the estimated transmission rate, we will pull the projections for future transmission from the Imperial model as well as IHME. Both models build projections under varying scenarios (e.g. reducing transmission by requiring masks) and will help us examine potential risks in the future. If there is a projected spike in virus transmission, we may decide to suspend activities until after the transmission spike.
- While reviewing the data we will take into consideration the burden on HCWs and we will consider not conducting surveys during any spikes in COVID-19 transmission.
- It is important to note that the proposed contingency framework will be relying on model projections and country-reported data. All discussions and decisions will recognize the challenge of modeling for an entire country (i.e. lack of sub-national projections), COVID-19 testing, and data reporting systems.

3.2 Infection Control Procedures

For each activity, we will implement WHO guidelines on prevention and control of infection as follows:

- Training sessions will be held outdoors whenever possible
- All participants in the training sessions will be required to wear masks and observe social distancing measures (2 meters). Masks will be provided for all study personnel and gloves for trainers to pass out tablets
- Study staff and data collectors will not attend training if they have or are presenting with flu-like symptoms. Study staff and data collectors will be screened ahead of training. We will only invite those who have not experienced COVID-19 symptoms and we will ask for them to not attend training or data collection if they do experience symptoms
- alcohol-based hand sanitizer and disinfectant will be provided to study team and health facility staff. In addition, soap and water or alcohol-based hand sanitizer will be easily accessible at study sites
- All training session attendants will be required to wash their hands with soap and water or alcoholbased hand sanitizer at the beginning of each day, at regular intervals throughout the day. Handwashing will also be required before and after any refreshments.
- Sufficient training materials and office supplies will be provided to prevent sharing among training participants
- All surfaces will be disinfected before and after each day's training or data collection
- Tablets will be disinfected before and after each use

- Data collectors will visit the site at the quietest time of day to minimize contact with facility staff and community members
- Data collectors will be required to wear masks and social distancing of 2 meters will be required when in the facility. If the facility itself does not allow for social distancing, the training and registry data extraction will occur outside where it will be possible.
- In training recommendations, we will let folks know not to come if they have symptoms. We will only invite those without symptoms and confirm they only attend if they don't have symptoms. Study staff will ask participants to opt-out if they develop symptoms. Data collectors will be sent home if they present with flu-like symptoms
- Prior to entering the facility, at regular intervals throughout, and at the days end, data collectors will be required to wash their hands with alcohol-based hand sanitizer
- For data collector's relying on public transportation to the participating facilities, alternative options will be discussed to minimize risk

4 Ethical Considerations

4.1 Informed Consent and Confidentiality

In accordance with Ethics Guidelines for Health Research Involving Human Participants in Cameroon and CHAI's Human Research Guidelines, we are seeking approval from CHAI's internal Scientific and Ethics Review Committee (SERC) and the National Ethics committee in Cameroon.

All HCW's who participate in the HCW surveys will provide informed consent. All study staff, including data collectors, will undergo ethical training sessions. In order to ensure confidentiality, all data collectors will sign a confidentiality agreement. Their activities and data safety measures will be supervised in the field by study managers.

4.2 Potential Risks for Participants

As the purpose of this work is to assess the integration of birth dose vaccination into the maternity process, there is no specific physical or psychological harm for participants. Personal information such as name will not be gathered in surveys; there is minimal risk to participants' data being identified. Child-level data from birth registries may have names of the children included but the names will be removed from the database, thus all datasets will be de-identified. The data will be kept on a secure server and only accessed by study staff using password encrypted computers.

4.3 Benefits for Participants

As the pilot include capacity building for service integration, HCW's will benefit from training and supportive supervision. Newborns born in participating health facilities during the study will benefit from immunization and protection from potential infections. In addition, the data and report will potentially benefit the

population health of Cameroon as the findings will contribute towards strengthening the service delivery of birth vaccines.

5 Study Tools

5.3 Data collection tools

HCW Questionnaire

Facility Health Care Worker Survey Questionnaire

Facility ID: _____

Instructions: Please pay close attention to the instructions of the question as not everyone is eligible for these questions. Additionally, please pay close attention to the skip patterns.

Section I: Consent					
NO.	QUESTION		RESPONSE CODE	SKIP	
НСW -1.1	DID YOU ADDRESS ALL THE QUESTION THAT THE FACILITY HCW HAD DURING THE CONSENT PROCESS?		Yes1 No2	IF NO, PLEASE GO BACK AND ANSWER QUESTIONS.	
HCW -1.2	IS THE FACILITY HCW OVER THE A	ge of 18?	Yes1 No2	IF NO, THANK AND END SURVEY	
HCW -1.3	DID YOU OBTAIN VERBAL CONSENT FROM THE FACILITY HCW?		Yes1 No2	IF NO, THANK AND END SURVEY	
Section I: S	Site Information				
NO.	QUESTION		RESPONSE CODE	SKIP	
ID1	RECORD SURVEY START TIME				
ID2	SELECT THE REGION	REGION 2			
	Survey CTO	KEGION 3			
ID3	Select if the area is urban or semi-rural	-			

ID4	SELECT IF THIS IS A PUBLIC OR PRIVATE FACILITY	PUBLIC 1 PRIVATE FOR PROFIT 2 PRIVATE FAITH-BASED 3	
ID5	PLEASE SELECT THE FACILITY LEVEL	Level 1: (Regional and referral hospital) . 1 Level 2: (District, CMA some faith-based). 2 Level 3: (IHC, HC)	
ID6	SELECT THE HEALTH FACILITY NAME Select the name in Survey CTO	FACILITY 1	
ID7	ENUMERATOR ID Select your name	NAME 1 1 NAME 2 2 NAME 3 3 NAME 4 4 NAME 5 5 NAME 6 6	
ID8	SUPERVISOR ID Select your supervisor's name	NAME 1 1 NAME 2 2 NAME 3 3 NAME 4 4 NAME 5 5 NAME 6 6	
Section 2:	Facility and respondent detai	ls	-
NO.	QUESTION	RESPONSE CODE	SKIP
FD1	OVERALL POPULATION OF THE HEALTH AREA	[] CATCHMENT POP DON'T KNOW	
FD2	WHAT IS YOUR PRIMARY JOB TITLE?	FACILITY IN-CHARGE	

FD3 FD4	WHAT UNIT ARE YOU WORKING IN? Read out loud and select most appropriate HOW LONG HAVE YOU BEEN WORKING IN MATERNITY AND/OR EPI UNIT? Select most appropriate combined experience in	MATERNITY. 1 IMMUNIZATION 2 BOTH MATERNITY AND IMMUNIZATION 3 OTHER (SPECIFY) 6 LESS THAN 6 MONTHS 1 6 - 12 MONTHS 2 12 - 24 MONTHS 3 24-36 MONTHS 4 OVER 36 MONTHS 5	
FD5	ONE OR both units HOW MANY YEARS HAVE YOU BEEN STATIONED AT THIS HEALTH FACILITY?	[]NUMBER OF YEARS IF LESS THAN 10	
SECTIO	N 3: HCWs knowledge		
NO.	QUESTION	RESPONSE CODE	SKIP
В1	According to EPI norms and standards, what are the vaccines that are administered before the 6 week immunization visit? (Do not probe, select all that apply)	OPV0	Select all that apply $A \rightarrow Answer$ B2 $B \rightarrow Answer$ B3 $C \rightarrow Answer$ B4 D-X \rightarrow B5
В2	IN AN IDEAL SITUATION, WHEN SHOULD OPVO VACCINE SHOULD BE ADMINISTERED TO A NEWBORN INFANT, ACCORDING TO EPI NORMS AND STANDARDS? (Read out loud and have the participant select most appropriate)	WITHIN 24 HOURS OF BIRTH	
В3	IN AN IDEAL SITUATION, WHEN SHOULD BCG VACCINE SHOULD BE ADMINISTERED TO A NEWBORN INFANT, ACCORDING TO EPI NORMS AND STANDARDS? (Read out loud and have the participant select most appropriate)	Within 24 hours of birth 1 After 24 h of birth but within two weeks of birth 2 Six weeks of birth 3 After six weeks of birth 4 Don't know 99	

B4	HOW MANY CHILDREN NEED TO BE PRESENT FOR A VIAL OF OPV TO BE OPENED?	[]No. of children Don't Know99	
B5	HOW MANY CHILDREN NEED TO BE PRESENT FOR A VIAL OF BCG TO BE OPENED?	[]No. of children Don't Know99	
B6	IF YOUR FACILITY PROVIDES HEPB VACCINE AT BIRTH, HOW MANY CHILDREN NEED TO BE PRESENT FOR A VIAL OF HEP B TO BE OPENED?	[]No. of children Does not provide HepB birth dose98 Don't Know99	
B7	IS IT RECOMMENDED TO ADMINISTER BCG AT BIRTH TO HEALTHY AND CLINICALLY STABLE LOW BIRTH WEIGHT INFANTS (<2500 GRAMS)?	Yes1 No2 Don't Know99	
B8	IS IT RECOMMENDED TO ADMINISTER OPVO AT BIRTH TO HEALTHY AND CLINICALLY STABLE LOW BIRTH WEIGHT INFANTS (<2500 GRAMS)?	Yes	
	•		
SECTIO	ON 4: General Unit information on	Birth Dose	
SECTIONO.	ON 4: General Unit information on QUESTION	Birth Dose RESPONSE CODE	SKIP
			SKIP
NO.	QUESTION HOW MANY HCWS WORK ON THE	RESPONSE CODE []]	SKIP
NO. CA1	QUESTION HOW MANY HCWS WORK ON THE MATERNITY UNIT? HOW MANY HCWS WORK ON THE	RESPONSE CODE [] No. of HWs Don't Know 99 [] No. of HWs	SKIP

CA5	How does the facility inform MOTHERS ABOUT THE BIRTH DOSE VACCINES? Do not read list. Select all that apply WHAT INFORMATION DO YOU	Pamphlet A Posters	
CA6	PROVIDE TO MOTHERS ABOUT THE BIRTH DOSE VACCINES? Do not read list. Select all that apply	ImportanceB Side effectsC OtherD No information providedX	
CA7	WHAT ARE THE CHALLENGES TO ADMINISTERING A BIRTH DOSE VACCINE WITHIN 24 HOURS OF BIRTH?	[Open-ended]	
CA8	WHERE ARE VACCINES STORED IN THIS FACILITY? Read list. Select all that apply	In Maternity A In EPIB Office of facility in chargeC Other (Please specify)X Don't KnowY	
CA9	PLEASE SELECT HOW THE VACCINES ARE STORED FOR EACH LOCATION LISTED ABOVE Read list. Select all that apply	A: In Maternity Fridge A Cold Box B Cool Water Pack C Fridge tag D B: In EPI Fridge Fridge tag B Cold Box B Cool Water Pack C Fridge A Cold Box B Cool Water Pack C Fridge tag D C: Office of facility in-charge Fridge A Cold Box B Cool Water Pack C Fridge A Cold Box B Cool Water Pack D	
CA10	Does this facility keep the oxytocin or Vitamin K cold?	A: Oxytocin Yes 1 No 2 Do not have Oxytocin 3 Don't Know 9 B: Vitamin K 9 Yes 1 No 2 Do not have Vitamin K 3 Don't Know 9	A →1 answer CA12, CA13, CA14 B→1 Answer CA14, CA15, CA17 Otherwise, skip to CA18

NO.	QUESTION		RESPONSE CODE	SKIP
SECTIO	ON 5: HCW perspectives			
CA19	WHAT DOES THE MOTHER PAY FOR VACCINATION BOOKLET/CARD?		let []cost Know99	
CA18	IF A VACCINE NEEDED TO BE ACCESSED LATE AT NIGHT OR ON THE WEEKEND, COULD MATERNITY STAFF ACCESS IT?	No		
CA17	Does the maternity unit staff have 24/7 access to vaccines in the immunization unit?	No	1 	
CA16	WHO IS RESPONSIBLE FOR ADMINISTERING VITAMIN K IN THIS FACILITY? Do not read list. Select all that apply	Midw Mater Other	orA rifeB rnity staffC r (Please specify)X KnowY	
CA15	HOW THE IS THE VITAMIN K KEPT COLD? Do not read list. Select all that apply	Cold E Cool V Do no Other	eA BoxB Water PackC ot have Vitamin KD r (Please specify)X r KnowY	
CA14	WHERE IS VITAMIN K STORED IN THIS FACILITY? Do not read list. Select all that apply	In EPI Office Other	aternity A B e of facility in chargeC r (Please specify)X E KnowY	
CA13	WHO IS RESPONSIBLE FOR ADMINISTERING OXYTOCIN IN THIS FACILITY? Do not read list. Select all that apply	Midw Mater Other	orA vifeB rnity staffC r (Please specify)X : KnowY	
CA12	HOW THE OXYTOCIN IS KEPT COLD? Read list. Select all that apply	Cold E Cool V Other	eA BoxB Water PackC r (Please specify)X : KnowY	
CA11	WHERE IS THE OXYTOCIN STORED? Do not read list. Select all that apply	In EPI Office Do no Other	e of facility in charge	

E1	WHAT CONCERNS DO YOU HAVE ABOUT ADMINISTERING OPVO WITHIN 24 HOURS OF BIRTH? Do not read list. Select all that apply	Adverse events following immunization A Inadequate personnel trainingB Inadequate guidance (SOPs)C Uncertainty on contraindicationsD Multiple vaccines administered togetherE No concernsF Other (please specify)X		
E2	WHAT CONCERNS DO YOU HAVE ABOUT ADMINISTERING BCG WITHIN 24 HOURS OF BIRTH? Do not read list. Select all that apply	Adverse events following immunization A Inadequate personnel trainingB Inadequate guidance (SOPs)C Uncertainty on contraindicationsD Multiple vaccines administered togetherE No concerns		
E3	WHAT BARRIERS HAVE YOU FACED WHEN EDUCATING MOTHERS ABOUT THE BIRTH DOSE VACCINES? Do not read list. Select all that apply	Mothers think education is a waste of timeA Custom of sequestering new-bornsB Not enough time during visitsC Lack of appropriate education materials for mothersD No barriersE Other (please specify)X		
SURVEY RE	ESULT			
NO.	QUESTION	RESPONSE CODE	SKIP	
RESULT	Record the result of the survey.	Survey complete		
	Record ending time of the survey			
DATA COLLECTOR COMMENTS				
NO.	QUESTION	RESPONSE CODE	SKIP	

	Record any comments that you have about the survey,	
Comments	particularly anything that may have affected the survey	
	completion or quality of data entry or the survey	

Immunisation register extraction

Immunization register extraction

Facility ID: _____

Date: _____

Please collect data until 30 entries are complete (all dates included) using sampling interval with both date of birth AND date of administration. For sampling interval, count how many children are entered within a year of today's date. Divide this total number by 30 to get your sampling interval. For instance, if there are 300 children within the year, your sampling interval is 300/30 or 10. Therefore, you will enter every 10th child until you reach 30 children in total with both a birth date AND a date of administration.

Child number	Q1. Date of Birth	Q2. Date of OPV0	Q3. Date BCG
		administration	administration
1	A - Date of birth listed.	A – Was vaccine	A – Was vaccine
	1 = Yes, 2 = No (If no, skip	administered?	administered?
	Q1.B)	1 = Yes, 2 = No (If no, skip	1 = Yes, 2 = No (If no, skip
		Q2.B)	Q3.B)
	B - Date listed		
		B - Date listed	B - Date listed

Delivery register extraction

Facility ID: _____

Date: _____

Does the register have the dates or administration listed for birth dose vaccines: 1 = Yes, 2 = No.

Does the register have the dates or administration listed for birth date: 1 = Yes, 2 = No.

For sampling interval, count how many children are entered within a year of today's date. Divide this total number by 30 to get your sampling interval. For instance, if there are 300 children within the year, your sampling interval is 300/30 or 10. Therefore, you will enter every 10th child until you reach 30 children in total. For this work you will also be looking the child up in the immunization register. Please ask the in-charge and the EPI nurse to gather this information when it is not in use.

	Delivery register			Immunization register									
Child Name	Q1. Date of Birth	Q2. Date of OPV0 administered	Q3. Date BCG administered	Q4. Were you able to find this child based on name	Q5. Date of OPV0 administered	Q6. Date BCG administered							
	A - Date of birth listed? 1 = Yes, 2 = No (If no, skip Q1.B)	A – Was vaccine administered? 1 = Yes, 2 = No (If no, skip Q2.B)	A – Was vaccine administered? 1 = Yes, 2 = No (If no, skip Q3.B)	and birth date in the register? 1 = Yes, 2 – No (if no, skip Q5 and Q6)	A – Was vaccine administered? 1 = Yes, 2 = No (If no, skip Q5.B)	A – Was vaccine administered? 1 = Yes, 2 = No (If no, skip Q6.B)							
	B - Date listed C – Time of Birth	B - Date listed C – Time of vaccine administration	B - Date listed C – Time of vaccine administration		B - Date listed C – Time of vaccine administration	B - Date listed C – Time of vaccine administration							

Newborn data tool

This form should be used to record data about each delivery during the study period. Data should be completed by a delivery nurse and shortly after the baby is discharged.

Child #:	Facility		Date:	//
	Code:			

Delivery Inform	nation	OPV0→	
Gender	Male1 Female2	OPV0	Yes1 No2
Date of birth, Time of birth, and birth weight	/ : : (DD/MM HH:mm) Grams	DATE AND TIME THE BABY RECEIVED OPVO	/ : : (DD/MM hh:mm)
CIRCLE ALL SERVICES PROVIDED	EPI visitA Dr visitB PNCC OtherX If other, specify:	IF NO, PLEASE CIRCLE THE PRIMARY REASON	Caregiver refused1Stock out2Scheduled for later3EPI was not open4Left before receiving the vaccine6Too few children to open a vial7Not eligible for clinical reasons8Not enough time for vaccination9Other10If other, specify:
OXYTOCIN GIVEN?	Yes1 No2	BCG→	
DISCHARGE DATE AND TIME	/ :	BCG	Yes1 No2
PLEASE LIST ANY CC	MPLICATIONS OR COMMENTS ON THE BIRTH:	DATE AND TIME THE BABY RECEIVED BCG	/ ::
		IF NO, PLEASE CIRCLE THE PRIMARY REASON	Caregiver refused

Notes for touchpoint calls

This form should be used to record any facility-specific information about the intervention including occurrence of stock outs, cold chain equipment challenges, or any unforeseen challenges that may have been discussed that relate to the intervention.

Area	Description

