2.7 Training Sessions

2.7.1 Intervention training

Training sessions will be held at each of the 15 facilities separately, with the same study members leading the sessions. Rather than a central training, we will conduct training at each facility, thus reducing mass gatherings during the COVID-19 pandemic. Please see the infection control section (Section 3.2) for COVID-19 related processes during training. At each individual training, all relevant and available health staff, including EPI focal points and maternity and newborn staff, will be asked to participate. In facilities where not all staff are able to attend training, we will ensure at least 1 staff member per shift is able to attend, to enable the information to be passed down to all staff members. During the touch points with the facility, staff will assess if the information was indeed passed down. The sessions will be split into two half day to prevent the facility from closing for a day and to allow for staff to be properly distanced. Moreover, training sessions will be held outside where possible. Ahead of training, a member of the study team will discuss potential training dates with the facility in-charge, ensuring dates occur when most convenient for the staff. The principal investigator will ensure that participants are comfortable throughout training and data collection. The training session will incorporate the below components.

Table 4: Summary of components included in training session

Training Component	Details
Maternity and newborn clinical protocols	 Knowledge reinforcement for topics relating to birth dose immunizations including: Immunization basics (Note: the HCW participating in the study are anticipated to be well-versed in this already, however we can leverage modules from Vaccination in Practice training to provide targeted refreshers based on the audience) Birth dose vaccine information for OPV0 and BCG including safety information and contraindications

	 Immunization technique including vaccine handling and site of administration Directly address hesitancy surrounding opening a multi-dose vaccine vial for only 1 baby by sharing PEV policy on opening vials for one child as well as training on practices to carry this out effectively (e.g. updating wastage rates in forecasts for ordering, calculating shelf life once opened, etc.) Reinforce incorporating birth dose conversations into routine antenatal care visits and adding messaging into ANC talking points 		

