2.10 Study Outcomes

The primary outcome of this pilot study is change in proportion of newborns receiving birth doses of BCG and OPVO within 24 hours. The key indicators from HCW surveys will be updated to include those from midline and end line surveys and will be sent for review prior to conducting those surveys.

Key Indicator	Source (data	Assessed at	Assessed at	Assessed
	collection tool)	baseline	midline	at end line
Average age of babies at time of	Birth registry and	×		×
receiving birth dose vaccines (BCG	immunization			
and OPV0)	record			
Proportion of babies born/received		×		×
in facilities receiving birth dose				
vaccines (BCG and OPV0) within 24				
hours				
The reason why BCG and OPV0 birth	Birth dose		×	×
dose vaccines were not administered	reporting form			
within 24 hours				
			×	×
			×	×
	HCW survey	×	×	×
Proportion of HCWs that know ideal		×	×	×
timing for birth dose vaccines				

Table 5. List of key indicators and sources

	×	×	×
Reported concerns with administering birth dose vaccines	×	×	×
within 24 hours			
Reported barriers to administering	×	×	×
birth dose vaccines within 24 hours			
Reported barriers to educating	×	×	×
caregivers on birth dose vaccines			
Maternity unit's access to birth dose	×	×	×
vaccines			

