2.12 Data Quality Control Measures and Security

All surveys will be completed in an electronic format using a tablet with incorporated skip patterns to confirm the highest quality data. All data to be stored on a secure server and accessed only by the study team. To minimize data collection errors, daily supervision of data entry into the tablets will be reviewed.

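### Items B2 and B3 are asked only of staff who name the vaccine unprompted at B1, so the Table 5 timing-knowledge indicator has no defined denominator, and the listed routing to B4 is faulty

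*Combined protocol and SAP*

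**What the plan says.** Section 5.3, HCW Questionnaire, Section 3, opens its knowledge items with an unprompted recall question, B1: "what are the vaccines that are administered before the 6 week immunization visit? (Do not probe, select all that apply". The skip column beside B1 sends option A to B2, option B to B3, option C to B4, and options D to X to B5. B2 asks the ideal timing of OPV0 and B3 the ideal timing of BCG; no other items ask about ideal timing. B4 reads "HOW MANY CHILDREN NEED TO BE PRESENT FOR A VIAL OF OPV TO BE OPENED", and B5 is the same question for BCG.

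The questionnaire's instructions treat routing as part of the design: "Please pay close attention to the instructions of the question as not everyone is eligible for these questions". Section 2.12 says surveys are completed in an "electronic format using a tablet with incorporated skip patterns".

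Table 5 (section 2.10) lists "Proportion of HCWs that know ideal" timing as an indicator at baseline, midline and end line. Section 2.11 promises means and proportions for the survey. It does not say who is in the denominator or how an unasked item is scored. Section 2.9.3 aims for at least 3 health workers per facility. Table 4 (section 2.7.1) includes birth dose information for OPV0 and BCG in the training, and a component to "Directly address hesitancy surrounding opening a multi-dose vaccine vial for only 1 baby".

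**The concern.** A proportion of health workers needs an answer, or a rule, for every health worker surveyed. On the printed form, a worker who does not think of BCG at B1 is not routed to the BCG timing item, and likewise for OPV0. The analyst then has two options, and each has a fault.

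- **Compute among those asked.** Entry to the denominator depends on recalling the vaccine. Training covers these vaccines and may raise recall, so the group asked can differ between rounds. Part of any change, or lack of change, would come from who was asked.
- **Count non-namers as not knowing.** The denominator is stable, but workers who know the timing and did not list the vaccine unprompted are misclassified. The indicator then mixes recall with timing knowledge.

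A baseline answer that was never collected cannot be recovered after training has begun. A second routing problem concerns B4, on OPV vial opening, which bears on a topic the training addresses.

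**Working it through.** The plan gives no target, expected value or sample size calculation for this indicator, so there is no figure to reproduce. The check has two parts.

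**1. Routing.** Following only the targets listed in the B1 skip column:

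| Named at B1 | Items listed |
|---|---|
| none of A, B, C | B5 |
| A | B2 |
| B | B3 |
| A and B | B2, B3 |
| C | B4 |
| A and C | B2, B4 |
| B and C | B3, B4 |
| A, B and C | B2, B3, B4 |

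A timing answer for OPV0 requires A, and one for BCG requires B. B4 appears only in the four rows that contain C. A worker who names just the two birth doses now in the programme (A and B) is not sent to B4.

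The B2 and B3 rows print no onward route. If interviewers simply ran on in order, A or B respondents would reach B4, but an A-only respondent would also be asked B3, against the condition that B leads to B3.

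**2. Size.** Inputs:
- Workers per round: 3 (section 2.9.3) x 15 facilities = 45, the intended minimum.
- Assumed, because the documents give no naming or knowledge rates: at baseline 27 name BCG and 24 of them give the right timing; at end line 43 name it and 41 are right.

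Asked only:
- Baseline 24/27 = 88.9%; end line 41/43 = 95.3%; change about +6 points.

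All 45, with the unasked bounded between none right and all right:
- Baseline: 24/45 = 53.3% to (24 + 18)/45 = 42/45 = 93.3%.
- End line: 41/45 = 91.1% to (41 + 2)/45 = 43/45 = 95.6%.
- Smallest change: (41 - 42)/45 = -2.2 points. Largest: (43 - 24)/45 = +42.2 points.

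All 45, with non-namers scored as not knowing:
- (41 - 24)/45 = +37.8 points.

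A second assumed case holds knowledge among namers near 70% while naming rises from 60% to 95%:
- Asked only: 19/27 = 70.4% to 30/43 = 69.8%, change -0.6 points.
- Non-namers scored as not knowing: 19/45 = 42.2% to 30/45 = 66.7%, change +24.4 points.

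If everyone names the vaccine in both rounds, all versions coincide and the gap is zero.

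**The case against.** The strongest reply is that Table 5 speaks of health workers without restriction, which read literally means all those surveyed; no section says the indicator will be computed among those asked. That is correct. A reader might infer that the indicator leaves out the least informed staff, but the documents do not establish this. It follows only under one of two possible rules, and the other has the misclassification fault.

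A reader might also infer a bias towards no change, with weak staff dropping out at baseline and re-entering later. The documents support neither part. The asked-only +6 lies inside the -2 to +42 range, so the direction is open. Section 2.9.3 does not say the same workers are surveyed in each round.

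Naming may also be high. Table 4 expects participating staff to know immunization basics already, and the problem shrinks as naming approaches 100%.

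On B4, it is tempting to conclude that knowledge of OPV vial policy goes unmeasured in the staff it concerns. That goes too far. The label of option C is not legible in the text available, and no onward route is printed after B2 or B3. Some Table 5 row labels are also missing, so B4's place among the indicators cannot be read. What stands is that the listed routing is incomplete and, taken as printed, bypasses B4 for A and B respondents. CA10 shows a similar slip: it sends oxytocin answers to CA12 to CA14, although the oxytocin items are CA11 to CA13.

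Finally, section 2.7.2 plans a field pilot with edits to the tools, and section 2.9.3 plans survey updates for later rounds. The printed form may therefore not be the final tablet logic. Neither section commits to this correction, and updates after baseline come too late for the baseline answers.

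**Conclusion.** The point holds in a limited form. On the printed form, timing knowledge is not collected from staff who do not name the vaccine, while Table 5 reports it as a proportion of health workers at three rounds with no denominator or scoring rule. The change reported could differ widely with the rule chosen: about +6 points among those asked, or about +38 with non-namers scored as not knowing. The true all-worker change could be anywhere from about -2 to +42. These figures rest on assumed naming and knowledge counts in 45 workers. They show how undetermined the indicator is and do not estimate a bias.

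That option A is OPV0 and option B is BCG is read from the content of B2 and B3. The B4 routing needs correction whatever option C stands for.

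This is a secondary indicator in a study whose outcomes are all descriptive. The primary outcome comes from the registers and is not touched. The change is still worth making, because it is cheap and baseline is the one round that cannot be repeated.

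**What to change.** Before baseline data collection:

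- Delete the skip rule at B1 and ask B2, B3, B4 and B5 of every respondent at baseline, midline and end line.
- Under Table 5, define the timing indicator separately for OPV0 and BCG, with all surveyed health workers as the denominator and a stated scoring rule for don't-know answers.
- Report unprompted naming at B1 as its own item.
- Use the tool pilot in section 2.7.2 to confirm that the tablet follows the corrected routing.

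The cost is one change to the form logic, a short addition under Table 5, and a few extra short questions for some respondents in a survey planned at one hour.
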